4.0 Treatment Assignment/Randomization

Study participants will be divided into three groups, appropriately equal in number:

- 1. Post-menopausal women with PFD on topical vaginal estrogen cream
- 2. Postmenopausal women with PFD on topical vaginal cream placebo (non-estrogen)
- 3. Premenopausal women with PFD

The postmenopausal women will be randomized to use topically applied vaginal estrogen or placebo using a random number generator.

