3.0 Study Population and Inclusion/Exclusion

It is anticipated that up to 30 female patients with Stage II or greater pelvic organ prolapse with planned gynecologic surgery at UTMB will be involved in this study with at least 15 participants completing the study, including at least 10 postmenopausal women, and at least 5 reproductive age women. Patients planning surgery for Stage II or greater pelvic organ prolapse may be eligible to participate. The study team will provide information about the study, including inclusion and exclusion, to clinic providers who may then inform their eligible patients about the study. If interested in learning more about the study, patients will be asked to speak with a study team member. The informed consent process will be completed in the clinic with a study team member authorized to

obtain study consent. During the consent process, patients are reminded of the voluntary nature of research participation; patients wanting to take part in the study are asked to sign the current approved study consent form. The completed written study consent form must be on file prior to a patient's participation in any study procedure.

Subjects must meet all of the inclusion criteria in order to participate in the study.

Inclusion criteria are:

- Females, 21 to 70 years of age, at the time of consent.
- Stage II or greater pelvic organ prolapse.
- Individuals who desire surgery to treat their PFD.
- Willing and able to comply with study procedures.
- Willing and able to provide written informed consent.

Subjects meeting any of the exclusion criteria at baseline will be excluded from study participation.

Exclusion Criteria are:

- Contraindication for estrogen use.
- Any medical condition that, in the opinion of the investigator, would place the subject at increased risk for participation.
- History of connective tissue disease
- Previous hysterectomy or pelvic organ prolapse surgery.
- Known allergic reaction to any agent under investigation or required by the protocol.
- Use of hormone therapy in postmenopausal women within the last 90 days.
- History of prior non-compliance or the presence or history of psychiatric condition (including drug or alcohol addiction) that would, in the opinion of the investigator, make it difficult for the subject to comply with the study procedures or follow the investigators instructions.
- Females who are pregnant or lactating.

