9.0 Study Withdrawal/Discontinuation

A study subject will be discontinued from participation in the study if any of the following occur:

- Unacceptable toxicity or serious adverse event
- Intercurrent illness, or other medical condition or situation occurs such that continued
 participation in the study would not be in the best interest of the subject in the opinion of the
 treating investigator
- Development of any exclusion criteria
- Subject withdrawals consent to continue in the research for any reason
- Vaginal bleeding of postmenopausal women on treatment cream

Handling of Withdrawals

Subjects who are agreeable may either undergo an exam and exit interview or complete the study procedures as previously described and completed in Study Visit 1 at the time of withdrawal from the study.

If a subject withdraws, a replacement subject may be recruited.

10. Statistical Considerations

This study will be a placebo-controlled, single center study with 3 arms of women planning on undergoing surgery for pelvic organ prolapse.

The primary outcome will be vaginal epithelial thickness based on OCT measures. Findings of collagen and elastin scores, epithelial/stromal/muscularis thickness, cytokines, MMPs, inflammatory cells, and receptors will be also compared between groups. Appropriate statistical analysis for ordinal (e.g. scores) and continuous (e.g. thickness) data will be applied, including tests to determine normality (Shapiro-Wilk) and analysis with ANOVA if criteria are met (e.g. normal, continuous). If ANOVA criteria are not met, then Kruskal-Wallis will be performed for non-normal, ordinal (e.g. scores) data sets.

Power Analysis

Preliminary and historical data are available for OCT thickness, therefore power analysis was based on differences in the OCT thickness mean difference between groups of 40 micrometers with standard deviation 18, and 80% power. Based on T-test and Bonferonni correction (alpha/number of tests = 0.025) for 2 comparisons (1. postmenopausal treatment vs placebo and 2. reproductive age women at 2 different stages of the cycle), five subjects were calculated to be needed per arm to be able to reject

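### Nothing stated in Section 4.0 secures the five women per randomised arm that Section 10 requires; the risk is material only if allocation is simple and enrolment stays near the minimum

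*Combined protocol and SAP*

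**What the plan says.** Section 4.0 sets the aim: "Study participants will be divided into three groups, appropriately equal in number". The method follows in one sentence: "The postmenopausal women will be randomized to use topically applied vaginal estrogen or placebo using a random number generator". No allocation ratio, block size, arm cap or list holder is given there, in the visit procedures of Section 5.0 or in the product description of Section 6.0.

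The numbers to be met come from two other places. The power analysis in Section 10 states that "five subjects were calculated to be needed per arm". Section 3.0 plans for "at least 15 participants completing the study, including at least 10 postmenopausal women, and at least 5 reproductive age women", within an upper limit of 30 women. Section 9.0 allows a withdrawn woman to be replaced but does not say which arm the replacement joins.

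Section 6.0 says that participants and study physicians are blinded, that the product carries a code number, and that a compounding pharmacy formulates both creams.

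**The concern.** The floor of 10 postmenopausal completers is exactly twice the five per arm, so it leaves no slack. The trial could meet that floor and still have four or fewer women in one arm, because an intention of equal groups is not a mechanism for producing them. Replacement does not repair this if the replacement's arm is left to chance.

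Estrogen against placebo is the only randomised comparison in the study. An uneven split costs it some power, and the cost is avoidable.

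**Working it through.** **Inputs.** Section 10 gives the effect, spread and power as "differences in the OCT thickness mean difference between groups of 40 micrometers with standard deviation 18, and 80% power", and the test as "Based on T-test and Bonferonni correction (alpha/number of tests = 0.025) for 2 comparisons". Sidedness is not stated; two-sided is assumed here. Section 3.0 gives the minimum of 10 postmenopausal completers and the maximum of 30 women. Simple 1:1 randomisation is an assumption about what the generator does.

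**1. The plan's own figure.** By the normal approximation, n per arm = 2 × SD² × (z₀.₉₈₇₅ + z₀.₈₀)² / difference² = 2 × 324 × (2.241 + 0.842)² / 1600 = 3.85, so 4. The stated five is consistent with this. With the noncentral t distribution, five per arm gives 76.0% power two-sided at 0.025 (six per arm gives 86.6%), or 86.7% one-sided.

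**2. Chance of each split with 10 women.** The number in one arm is Binomial(10, 0.5).
- 5:5: 252/1024 = 24.6%
- 4:6 either way: 420/1024 = 41.0%
- 3:7 or worse: 2 × (1 + 10 + 45 + 120)/1024 = 352/1024 = 34.4%
- An arm of two or fewer: 2 × (1 + 10 + 45)/1024 = 112/1024 = 10.9%

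**3. Power by split.** The noncentrality is difference / (SD × √(1/n₁ + 1/n₂)), with 8 degrees of freedom for every split of 10. At 5:5 and 40 um it is 40 / (18 × √0.4) = 3.51.

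| Split | Probability, both directions | Power, 40 um | Power, 80 um |
|---|---|---|---|
| 5:5 | 24.6% | 76.0% | 99.98% |
| 4:6 | 41.0% | 74.1% | 99.97% |
| 3:7 | 23.4% | 67.9% | 99.9% |
| 2:8 | 8.8% | 55.1% | 99.2% |
| 1:9 | 2.0% | 32.4% | 89.9% |
| 0:10 | 0.2% | 0% | 0% |

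Averaged over the splits, power is 70.5% at 40 um and 99.5% at 80 um. The 80 um column uses the expected means in the Section 10 example, 180 um with estrogen less 100 um without.

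**4. Chance that both arms reach five, by number randomised, no dropout.**
- 10: 24.6%
- 11: 924/2048 = 45.1%
- 12: (792 + 924 + 792)/4096 = 61.2%
- 15: 88.2%
- 20: 1 − 2 × 6196/1048576 = 98.8%

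The protocol gives no dropout rate. At 20 randomised, assumed dropout of 10%, 20% and 30% gives 96.2%, 89.8% and 76.5% for five completers in both arms. At 12 randomised, assumed dropout of 10% and 20% gives 40.0% and 20.5%.

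**The case against.** A reader might infer that the protocol prescribes unrestricted randomisation of about 10 women and will therefore usually miss five per arm. The documents do not support that, for two reasons. A random number generator is a tool that can equally produce a blocked list, and the same section states an intention of equal groups; simple randomisation is a reading of silence. And 10 is a floor on completers, not the number assigned: "It is anticipated that up to 30 female patients with Stage II or greater pelvic organ prolapse" may take part. If the three groups were equal thirds of 30 (an assumption), about 20 women would be randomised and a shortfall without dropout would be rare, at 1.2%. A shortfall is more likely than not only at 10 or 11 randomised.

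The power cost can also be overstated. The most likely split, 4:6, costs about 2 points against 5:5, and the average loss is about 5.5. Even a perfect 5:5 gives 76% two-sided rather than 80%, and balancing the arms does not remove that gap. At 80 um the loss is under 1 point down to 2:8. Nor does a small arm leave almost no usable variance: a pooled t-test on 10 women has 8 degrees of freedom whatever the split.

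All of this stands, and it limits the size of the point. It does not answer the gap itself. The limit of 30 is a ceiling, while 10 completers is the only stated minimum. The 80 um figure comes from the worked example, whereas the sample size was computed for 40 um. If a blocked list is already intended, stating it costs one sentence.

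**Conclusion.** The point holds as a gap in specification with a conditional and modest consequence. The protocol requires five per arm and states nothing that enforces it.

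The unfavourable figures (5:5 in 24.6% of cases, 3:7 or worse in 34.4%, average power of 70.5% against 76.0%) rest on four assumptions: simple 1:1 randomisation, exactly 10 women assigned, no dropout, and a two-sided test at 0.025 for 40 um with SD 18. Under simple randomisation, two changes shrink the problem. With more women assigned, both arms reach five in 61% of cases at 12 and 98.8% at 20. With the 80 um difference of the worked example, power is at least 99% for any split down to 2:8. The documents use both 40 um and 80 um for this contrast, so the power loss is best reported as a range between the two. The change is worth making because it is cheap, not because the trial would otherwise probably fail.

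**What to change.** In Section 4.0, state that postmenopausal women are allocated 1:1 to estrogen or placebo from a computer-generated permuted-block list with small varying blocks (for example 2 and 4). The list should be built so that the arms are equal at the planned number. That condition matters: if block sizes of 2 and 4 are drawn at random with equal chance, stopping at 10 can fall inside a block and give 6:4 about 11% of the time. The compounding pharmacy prepares and holds the list, concealed from the study physicians.

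In Section 9.0, state that a replacement takes the withdrawn woman's arm, assigned by the pharmacy under the blind, so that at least five per arm complete. Blocking alone balances the numbers randomised, not the numbers completing.

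The cost is a few sentences, a different list and a list-holding task for the pharmacy, which the protocol does not now assign to it. There is a small downside: the end of a block becomes slightly predictable if earlier assignments were unblinded, and a replacement's arm could be guessed if the withdrawn woman's arm had become known. Varying block sizes and concealment at the pharmacy limit this.

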5.0 Study Procedures

Postmenopausal Women

Study Visit 1

Within approximately 30 days of the scheduled surgery date, the postmenopausal subjects will come to the Pelvic Health Clinic at Victory Lakes to have an optical coherence tomography (OCT) scan and pelvic floor (endovaginal) ultrasound.

Both of these tests involve a vaginal probe being inserted in the vagina to collect pelvic organ and tissue images. The OCT produces higher resolution 3-dimensional images and takes 10-15 minutes or less and the endovaginal ultrasound takes about 30-45 minutes.

At this visit, up to 20ml of blood may be drawn for serum hormone levels of estradiol and testosterone, DHEA and androstendione.

Subjects will complete Uro Gyn Clinical Intake Form if not previously within 3 months. The Intake Form includes the following questionnaires: UDI-6, POPDI-6, CRADI-8, PFIQ, PISQ-12 (see protocol appendix for questionnaries).

Subjects will be randomized to placebo or estrogen vaginal cream.

Subjects will be provided with a topical vaginal cream to use daily until 2 days prior to your scheduled surgery date (4-6 weeks). Subjects will apply 0.5 gram of the study vaginal cream daily. Subjects will be given a study diary as a reminder and to record usage and will return their spent tube of cream for weighing as a measure of compliance.

Study Visit 2

Subject will return within a week prior to schedule surgery. Subjects will repeat the OCT, pelvic floor ultrasound and the questionnaires as done in Study Visit 1. Up to 20ml of blood may be drawn to repeat serum hormone levels of estradiol and testosterone, DHEA and androstendione.

Premenopausal Women

Study Visit 1

Premenopausal subjects will have their studies visits 1 scheduled in order to coincide with the subject's follicular or luteal phase of their menstrual cycle. Study visit 2 will be scheduled in order to coincide with opposite phase from study 1.

Premenopausal subjects will come to the Pelvic Health Clinic at Victory Lakes to have an optical coherence tomography (OCT) scan and pelvic floor (endovaginal) ultrasound.

Both of these tests involve a vaginal probe being inserted in the vagina to collect pelvic organ and tissue images. The OCT produces higher resolution 3-dimensional images and takes 10 minutes or less and the endovaginal ultrasound takes about 30 minutes.

At this visit, up to 20ml of blood may be drawn for serum hormone levels of estradiol and testosterone, DHEA and androstendione. Urine or serum pregnancy test will be performed for patients at risk of pregnancy at the discretion of the study gynecologist.

Subjects will complete Uro Gyn Clinical Intake Form if not previously within 3 months. The Intake Form includes the following questionnaires: UDI-6, POPDI-6, CRADI-8, PFIQ, PISQ-12 (see protocol appendix for questionnaries).

Study Visit 2

Subject will return within a week prior to schedule surgery. Subjects will repeat the OCT, pelvic floor ultrasound and the questionnaires as done in Study Visit 1. Up to 20ml of blood may be drawn to repeat serum hormone levels of estradiol and testosterone, DHEA and androstendione.

Surgical Tissue Collection

After anesthesia and prior to vaginal preparation for surgery, vaginal fluid (secretions) will be collected similar to getting a pap smear and vaginal rinse with saline will be performed and up to 30ml of the rinse material or lavage will be collected for research to look at cytokines and vaginal microflora.

The surgical tissue that is excised and removed is standard for the surgery performed, and typically this tissue is discarded after surgery. The tissue collected for this research is discarded surgical tissue, about 2-4 postage stamps in size, depending on whether anterior and/or posterior surgical repair is performed.

The surgery will proceed as scheduled and tissue from the vagina will be collected and processed for further tissue analysis. The tissue collected will be the tissue that is typically discarded during the surgery.

Vaginal Secretion and Vaginal Fluid Analysis

Vaginal secretions and lavage fluid will be transported to [name] lab and to Oak Crest Institute of Science and will be evaluated for cytokines, including IL-6, TNF- α , TNF- β , evidence of inflammatory cells, and vaginal microflora using an extended qPCR panel developed with an ITS Novel Methods Grant ([name], [name], 2012).

Vaginal Tissue Analysis

After excision, vaginal tissue will be sectioned into ~3mm pieces and preserved for analysis in formalin, RNALater, and frozen at -80C for future analysis. Formalin preserved sections will be paraffinembedded and stained with H&E (epithelium, stroma, muscularis assessment), Masson's trichrome (collagen, vessel endothelium), Hart's (elastin), or IHC stained for MMPs, estrogen, progestin, and testosterone receptors and CD68 (macrophage). A trained pathologist will interpret the images and provide grading of findings of epithelium, muscularis, collagen, elastin, and IHC findings for presence of MMPs, hormone receptors, and macrophages. Fresh tissue will also be imaged using noninvasive imaging with optical coherence tomography (epithelial and stromal thickness) and multiphoton/SHG imaging (collagen structure) through collaboration with the CBME. Samples in RNALater will be shipped to Oak Crest Institute of Science for evaluation of the transcriptome.

Oak Crest Institute of Science will provide testing and analysis for this study. In addition, coded specimens and data (not having personal identifiers) may be used in ongoing collaborative research with [name] of Oak Crest.

Ultrasound and OCT

Pelvic floor ultrasound will be performed using a standard clinical BK ultrasound system with abdominal, endovaginal, and 3D rotational (vaginal) probes. OCT imaging will be performed using an FDA-approved Niris OCT system (Imalux, Cleveland, OH). OCT images will be collected by direct tissue contact with the 2.7mm diameter probe that will be covered with a sterile disposable sheath and cleaned between use with Cidex. OCT images will be obtained using guidance with a colposcope and a magnetic (GPS) positioning system to record the location of the images collected. Digital images of the cervix and vagina will also be obtained with a digital camera for localization of images.

Parameters measured by ultrasound will include: vaginal thickness, muscularis thickness/volume, vaginal and uterine blood flow (flow and resistive index), levator ani muscle thickness/volume, uterine/cervical descent. Parameters measured by OCT will include vaginal epithelial and stromal thickness. Women will be measured before vaginal treatment with estrogen and 4 weeks after estrogen (or no estrogen) treatment.

The excised tissue will also be evaluated with high resolution imaging methods of OCT and multiphoton/second harmonic generation.

Medical Record Review

The medical record will be reviewed for demographics, medical/surgical history, hormonal status, medications, BMI, and tobacco status.

Tissue Banking

A portion of the subject's blood sample and surgical specimen may be banked at the Biorepository on the UTMB campus for future analysis or used in other approved research at UTMB. Specimen storage or banking involves transferring specimens into several smaller coded sample tubes for freezing and storage in the research.

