7.0 Potential Risks and/or Discomforts of Participation

Topical Vaginal Cream: Allergic reaction; Irritation or other discomfort; Vaginal burning; Vulvar-vaginal infection; Vaginal bleeding; Increased vaginal discharge; Trauma from applicator; Headache; Breast tenderness.

OCT – Possible discomfort with the probe in connection with the evaluation. Some women have reported minor irritation, redness and vaginal bleeding.

Pelvic floor (endovaginal) ultrasound – The test is usually painless although some women have reported mild discomfort from the pressure of the probe. There are no known harmful effects on humans.

Blood Draw – The discomfort associated with drawing blood from a vein is a light pinch or pinprick at the puncture site. The risks include possible bruising and swelling around the puncture site; less commonly, infection, small blood clot or bleeding at the puncture site and faintness from the procedure.

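### The order of cycle phases in the premenopausal women is neither assigned nor balanced, so the follicular-luteal contrast is partly confounded with first versus second scan, and fully so if all five women share one order

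*Combined protocol and SAP*

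**What the plan says.** Section 5.0 (Premenopausal Women, Study Visit 1) leaves the starting phase open: "Premenopausal subjects will have their studies visits 1 scheduled in order to coincide with the subject's follicular or luteal phase of their menstrual cycle". It then fixes the second scan relative to the first: "Study visit 2 will be scheduled in order to coincide with opposite phase from study 1". Under Study Visit 2 the timing is anchored to the operation: "Subject will return within a week prior to schedule surgery".

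Section 4.0 describes the only random assignment in the trial: "The postmenopausal women will be randomized to use topically applied vaginal estrogen or placebo using a random number generator". It does not cover the order of phases.

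Section 10 states: "The primary outcome will be vaginal epithelial thickness based on OCT measures". Its Power Analysis applies a "Bonferonni correction (alpha/number of tests = 0.025) for 2 comparisons", the second being "reproductive age women at 2 different stages of the cycle", with expected means of 240 um (follicular) and 200 um (luteal). The analysis text names ANOVA or Kruskal-Wallis. It names neither a paired model nor a term for visit or order.

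**The concern.** Within each woman, phase and visit number are tied: if one scan is follicular and first, the other is luteal and second. This is a two-period within-woman comparison, and the protection such a design normally has is a controlled order. Here the order follows from scheduling. Because the second scan must fall shortly before surgery, the surgery date settles the phase at Visit 2, and so the starting phase, unless someone plans otherwise.

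If the orders are lopsided, anything that changes between a first and a second scan enters the phase difference: operator familiarity, drift in reading, or a reaction to the first contact scan (Section 7.0 says of OCT: "Some women have reported minor irritation, redness and vaginal bleeding"). At stake is one of the two comparisons for which the trial is sized. With all women in one order, no later analysis can separate visit from phase.

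**Working it through.** **Inputs.** From Section 10: difference 40 um, SD 18, alpha 0.025 per comparison, 80% power, five per arm. From Section 3.0: at least five reproductive age women completing. Not given, so assumed: the visit effect d, the within-woman correlation rho, and a two-sided test. The plan does not say whether SD 18 is per scan or the SD of the within-woman difference. Taken as per scan, the SD of the difference is s = 18 x sqrt(2(1 - rho)): 25.5 at rho = 0, 18.0 at 0.5 and 11.4 at 0.8.

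**The plan's own figure.** Five per arm is in the right range. The normal approximation gives 4. At n = 5 the exact two-sided power at 0.025 is 76.0% for a two-sample t-test and 85.9% for a paired t-test with s = 18. The two alphas sum to 0.025 + 0.025 = 0.05, so the phase contrast carries half.

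**Bias.** Let d be the mean change from first to second scan that is unrelated to phase. In a luteal-first woman the follicular-minus-luteal difference gains d; in a follicular-first woman it loses d. With n1 and n2 women in the two orders, the absolute bias is d x |n1 - n2| / n:
- 5:0 gives 5/5 = 1.0d
- 4:1 gives 3/5 = 0.6d
- 3:2 gives 1/5 = 0.2d

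**Type I error, paired t-test, n = 5, no phase effect, d = 10 um.** At 5:0 the statistic is noncentral t with 4 df and noncentrality d x sqrt(5)/s, that is 0.88, 1.24 and 1.96 for the three correlations. The critical value is 3.495. The 4:1 and 3:2 rows are simulated.

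| Order | rho = 0 | rho = 0.5 | rho = 0.8 |
|---|---|---|---|
| 5:0 | 5.7% | 9.1% | 20.1% |
| 4:1 | 3.0% | 3.3% | 3.6% |
| 3:2 | 2.0% | 1.6% | 0.8% |

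With mixed orders the visit effect also enters the spread of the differences, which holds the rejection rate down. At 5:0 with d = 5 the rates are 4.1% (rho 0.5) and 6.5% (0.8); with d = 20 they are 31% and 67%. In the other direction, an opposing d of 10 um at 5:0 turns a true 40 um into 30 um, and power falls from 85.9% to 62% (s = 18).

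**If order fell by coin toss** (illustrative, since scheduling is not a coin):
- P(5:0) = 2/32 = 6.25%; P(4:1) = 10/32 = 31.25%; P(3:2) = 20/32 = 62.5%.
- Average type I error at d = 10, rho 0.5: 0.0625 x 9.1% + 0.3125 x 3.3% + 0.625 x 1.6% = 2.6%. At rho 0.8: 0.0625 x 20.1% + 0.3125 x 3.6% + 0.625 x 0.8% = 2.9%.
- At d = 20, rho 0.5: 0.0625 x 31.3% + 0.3125 x 3.3% + 0.625 x 0.4% = 3.2%.
- Average absolute bias: 0.0625 x 1.0d + 0.3125 x 0.6d + 0.625 x 0.2d = 0.375d.

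**Cost of a visit-adjusted test.** The mean of the two order-specific means has standard error (s/2) x sqrt(1/n1 + 1/n2). At 3:2 and s = 18 this is 9 x sqrt(0.833) = 8.22 with 3 df (critical value 4.177), against 18/sqrt(5) = 8.05 with 4 df for the paired test. For the same s the 97.5% half-widths are 34.3 and 28.1 um, a ratio of 1.22. Power for 40 um falls from 85.9% to 71.5%. With six women at 3:3 the adjusted test has 91.3%. At s = 25.5 the adjusted powers are 43.6% (3:2) and 65.1% (3:3).

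**The case against.** **No visit effect is documented.** This stands. Irritation is listed as a risk, but nothing says that it lasts until the opposite phase or alters epithelial thickness. Learning and drift run over roughly a year and up to 30 women, so only part falls between one woman's two scans, and colposcope guidance with position recording limits drift in location. Every figure with a numerical d is conditional on that assumption.

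**The 5:0 case is conjecture.** This also stands in part. No section says that surgery is booked by cycle phase, and by allowing both orders the plan avoids the fully confounded fixed-order design. A reader might infer that the contrast is confounded as designed, or that a 9 to 20% false-positive rate is to be expected. The documents support neither: those rates belong to 5:0 only. Nor should one pool 4:1 with 5:0 (12/32 = 37.5% under a coin toss) and attach the 5:0 rates to the total, since at 4:1 the test is close to nominal. What survives is that no rule prevents a lopsided order, and that bias at 4:1 is still 0.6d.

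**The placebo group offers a check.** Postmenopausal placebo women are scanned at both visits, so their change hints at a visit effect. It is a weak check: the tissue differs, a cream is applied in between, and with five women and s = 18 the 95% interval is about +/- 2.776 x 8.05 = 22 um, too wide to exclude d = 10.

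**The contrast is minor.** It is absent from the aims in Section 2.0 and from the groups in Section 4.0. That limits importance, but Section 10 still gives it half the alpha.

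**Conclusion.** The point holds as a modest, inexpensive design improvement. The starting phase has no assignment rule, and the planned analysis has no visit or order term, so the phase contrast carries between 0.2d and 1.0d of any visit effect with five women. The main harm is bias in the estimate: 2, 6 or 10 um for an assumed d of 10 um, against a planned difference of 40 um. Material inflation of the test for that d needs all five women in one order, which chance would produce in 6.25% of groups but scheduling could produce more often.

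The conclusion rests on an assumed d, a two-sided paired t-test, SD 18 per scan and correlations of 0 to 0.8. A reader might infer that the trial's treatment result is also in doubt. It is not: estrogen versus placebo is randomized between women and does not depend on phase order.

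**What to change.** **Section 5.0, Premenopausal Women.** Assign the starting phase alternately from a prepared list (3:2 with five women, 3:3 with six), book the research visits accordingly where the surgery schedule allows, and record the order actually achieved. This cuts the worst-case bias from d to 0.2d, and the chance-order average from 0.375d to 0.2d. A sixth woman removes the remaining 0.2d; Section 3.0 sets five as a minimum, so this fits the stated enrolment.

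**Section 10.** State that the phase contrast is tested within woman by the paired comparison, and report the phase difference separately by starting phase. Give the mean of the two order-specific means as a sensitivity analysis only, because with five women it has 3 df and falls short of the planned 80% power. State also whether SD 18 refers to a single scan or to the within-woman difference.

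**Cost.** One list, one recorded field, two or three sentences and some scheduling constraint. At 3:2 a bias of 0.2d remains in the primary estimate. The change has to be made before scanning starts, because a single shared order cannot be repaired afterwards.
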